sanofi-aventis Recherche & Développement
[name]
[name]

OTHER EMERGENCY TELEPHONE NUMBERS

CLINICAL TRIAL SUMMARY

COMPOUND: SAR407899	STUDY No.: ACT14656
TITLE	A randomized, double-blind, placebo-controlled parallel arm dose titration study to assess the effects of SAR407899 in patients with microvascular angina and/or persistent stable angina despite angiographically successful percutaneous coronary intervention (PCI).
INVESTIGATOR/TRIAL LOCATION	Europe, Asia and US
PHASE OF DEVELOPMENT	Phase 2a
STUDY OBJECTIVE(S)	
Primary objective:
 
 Assess the effects of SAR407899 on coronary vasomotor function using coronary flow reserve (CFR) in patients with microvascular angina and/or persistent stable angina despite angiographically successful PCI. 
Secondary objectives:
 
 Assess the effects of SAR407899 on quality of life using SAQ-PL in patients with microvascular angina and/or persistent stable angina despite angiographically successful PCI. Assess the safety of SAR407899 in patients with microvascular angina and/or persistent stable angina despite angiographically successful PCI with a focus on identified risks such as hypotension and orthostatic hypotension. Assess SAR407899 plasma concentrations in microvascular angina patients and/or persistent stable angina despite angiographically successful PCI.
STUDY DESIGN	A Phase 2a, multi-center, randomized with 1:1 ratio, double-blind, placebo-controlled parallel group study with weekly titration up to maintenance dose, based on individual patient tolerability, particularly symptomatic or asymptomatic blood pressure (BP) decreases.
STUDY POPULATION	Male and female patients with microvascular angina and/or persistent stable angina despite angiographically successful PCI.
Main selection criteria	
Main Inclusion criteria:
 
 Male or female patient not at childbearing potential ≥ 18 year-old or legal age of majority. Female patient if she has undergone sterilization at least 3 months earlier or is postmenopausal. 
 Post-menopausal status is defined by having no menses for 12 months without an alternative medical cause. In females not treated with hormonal replacement therapy (HRT), menopausal status is confirmed by a high follicle stimulating hormone (FSH) level greater than 40 IU/L. In females on HRT and whose menopausal status is in doubt (ie, in women aged less than 45 years), a highly effective contraception methods will be required.

	
Contraception should be used during the whole study and for at least seven days corresponding to time needed to eliminate study treatment.
 
• Symptomatic stable angina pectoris (typical or atypical symptoms with an average of at least bi-weekly episodes over the past month),• Patients with non-obstructive (<50% stenosis) coronary arteries or intermediate stenosis (between 50 and 70%) should have fractional flow reserve (FFR) >0.80 or instantaneous wave-free ratio (iFR) >0.89 on angiogram documented within the previous 24 months*. In patients with stenting, a minimum diameter stenosis of <10% is required. 
or
 
Coronary computed tomography angiography (CCTA) with finding of non-obstructive coronary arteries within the past 24 months* in patients without previous PCI.
 
*Note: in cases of clinically suspected progression of atherosclerosis as per the Investigator, a more contemporary (ie, 6 months) evidence should be provided.
 
or
 
CCTA performed during screening period, with finding of non-obstructive coronary arteries, in patients diagnosed with MVA and stable angina without previous PCI who did not have a coronary angiogram or CCTA in the previous 24 months but between 24 months to 5 years.
 
• Baseline global CFR (measured during the study) assessed by ¹³N-ammonia or ⁸²Rubidium PET scan <2.0. 
Main Exclusion criteria:
 
• Esophageal dysmotility or esophagitis.• Any use of nitrates (except short-acting nitrates) and/or dipyridamole and/or phosphodiesterase type 5 (PDE5) inhibitors within one week prior to baseline PET scan or anticipated to be used during the study.• Patients with acute coronary syndrome (ACS) [myocardial infarction (MI) and/or unstable angina] in previous 3 months.• Unsuccessful or incomplete coronary revascularization with residual obstructive stenosis or coronary artery disease (CAD) progression in native vessels as documented on invasive coronary angiography (≥50% stenosis) within 24 months of enrollment.• Patients with history of coronary artery bypass grafting (CABG).• Percutaneous coronary intervention performed at the time of an ACS (MI or unstable angina) in the previous 12 months.• Recent PCI within the past 3 months.• Contraindication to vasodilator stress PET scan and/or CCTA if CCTA needed during screening.• Regional local flow abnormal perfusion defects at baseline PET scan*. 
*Note: if contemporary evidence with invasive coronary

--	---

	angiography or CCTA demonstrates non-obstructive coronary arteries or if the regional local flow abnormal perfusion defect on PET scan is consistent with previous studies then patient qualifies for the study.
	
 • Recent (≤ 3 months) major surgery (ie, valvular surgery, surgery for congenital heart disease), stroke, transient ischemic attack (TIA), sustained ventricular arrhythmia, clinically significant structural heart disease (moderate-severe valvular disease, hypertrophic cardiomyopathy, congenital heart disease, pulmonary hypertension). • Patients with cardiac conduction abnormalities (second or third degree atrioventricular [AV] block, sick sinus syndrome, symptomatic bradycardia, sinus node disease) except in patients fitted with a functioning pacemaker. • History or known carotid stenosis: 
 - Carotid stenosis ($>50\%$) or - History of carotid stenosis in patients with previous symptoms. • Contraindication or known hypersensitivity to adenosine (or regadenoson). • Contraindication to aminophylline. • Inability to discontinue treatment with methylxanthines treatment within 24 hours prior to PET scan. • Patient unable to read, understand and fill a questionnaire without any help (eg, partially visually impaired or blind). • Systolic Blood Pressure (SBP) <110 mmHg at baseline. • Presence at baseline of symptomatic orthostatic hypotension (SBP decrease of 20 mmHg or more at Minute 3 or Minute 5 between seated and standing position), or asymptomatic orthostatic hypotension with a decrease in SBP equal or greater than 30 mmHg at Minute 3 or Minute 5 when changing from the seated to the standing position. • Renal impairment [estimated glomerular filtration rate (eGFR) <50 milliliter (mL)/min/1.73m² at screening and baseline]. • Drug-induced liver injury related criteria: 
 - Underlying hepatobiliary disease, - ALT >3 times the upper limit of normal (ULN).
Total expected number of patients:	78 patients to be randomized (39 per arm).
Expected number of sites:	Approximately 20 sites. Stratification on the presence of angiographically successful PCI (YES/NO) will be performed.
STUDY TREATMENT(s)	
Investigational medicinal product(s)	SAR407899, 2.5 mg and 5mg capsules. SAR407899 matching placebo.
Formulation:	Capsules.
Route(s) of administration:	Oral administration, twice per day: in the morning and at bedtime. Dose may be taken with or without food as per preference of the patient.

[figure not shown]

Dose regimen:
	
Starting dose: [REDACTED].
 
Individual dose titration based on BP tolerability at scheduled visits with the following rules:
 
 • [REDACTED] if well tolerated over a period of 3 weeks followed by a maintenance period of 1 week (total duration of treatment 4 weeks including titration).
	
[REDACTED]
 
[REDACTED]

	
 • If [REDACTED] dose is not tolerated, the study drug will be discontinued. 
Stopping criterion based on creatinine level:
 
 • Stop study drug if creatinine blood level >150 µmol/L and increase from baseline >30%. 
[REDACTED]. When 19 patients will have completed first week after randomization, the Data Monitoring Committee (DMC) will review the clinical safety data including adverse events of special interests (AESIs). During the safety evaluation of the first 19 enrolled patients, these patients will continue to receive IMPs as per the titration schedule described above and enrolment will continue.

Non investigational medicinal product(s)
	
 • PET radiopharmaceuticals (¹³N-ammonia and ⁸²Rubidium). • Vasodilator stressors (adenosine and regadenoson). 
The NIMPs for PET scan should be used according to their approved labeling.

ENDPOINTS
	
Primary efficacy endpoint:
 
 • Change from baseline to Week 4 in uncorrected global CFR assessed by ¹³N-ammonia or ⁸²Rubidium PET scan. 
Secondary efficacy endpoint:
 
 • Change from baseline to Week 4 on angina-induced physical limitation using SAQ-PL (disease-specific health-related quality of life). 
Exploratory endpoints:
 
 • Rate of diary angina episodes at baseline and Week 4 • Rate of diary angina episodes requiring use of short-acting nitrates at baseline and Week 4 • Change from baseline to Week 4 in the other dimensions of the SAQ. • Change from baseline to Week 4 in the SAQ-7 score. • Patients' perceptions of treatment and symptoms assessed at baseline and Week 4.

	
Safety:
 
 • Adverse events (AEs) / treatment-emergent adverse events (TEAEs). • Blood pressure and orthostatic blood pressure. • Blood creatinine and cystatin C. 
Pharmacokinetics:
 
 • Peak and trough SAR407899 concentrations at specific time points.

ASSESSMENT SCHEDULE
	
Coronary Flow Reserve assessed by ¹³N-ammonia or ⁸²Rubidium PET scan and SAQ will be assessed at baseline and the end of Week 4.
 
Safety will be monitored during the whole study with special focus on BP and renal function (creatinine and Cystatin C).
 
Pharmacokinetics: sparse sampling will be performed on Day 1 at 1 hour and 3 hour post-dosing, pre-dose on Day 8, Day 15 and Day 22, and pre-dose and in the 1-3 hour interval post-dose on Day 29.
 
Number of angina episodes and short acting NTG intake per week using a diary from baseline to Week 4.


STATISTICAL CONSIDERATIONS
	
Sample size determination:
 
Estimated as 78 patients (39 per group). Based on a large study of 2783 patients referred for rest/stress PET (1) which suggested a SD of 0.65 for CFR at baseline. Under the hypothesis of a correlation of 0.6 between baseline assessment and week 4-assessment the SD for the change from baseline to Week 4 could be estimated at 0.58.
 
35 patients per group will be needed to detect with 1 sided test alpha 0.05 and 80% power, a clinically significant relevant difference versus placebo of 0.35 in the change from baseline in PET CFR to Week 4.
 
To reach this number of patients 78 patients need to be included in this study with the hypothesis of 10% inevaluable.
 
Analysis population:
 
The efficacy population will be the modified intend-to-treat population, defined as all randomized patients analyzed according to the treatment group allocated by randomization, receiving at least one dose or part of a dose of the investigational medicinal product and having a baseline PET scan CFR assessment available.
 
The safety population will include all randomized patients who received at least one dose or part of a dose of the IMP. In the safety analysis, patients will be analyzed in the treatment group as actually received.
 
Primary analysis: efficacy analyses will be performed on ITT population.
 
The change in CFR from baseline to week 4 will be analyzed using an ANCOVA model. The model will include the two fixed categorical effect of treatment group (pooled SAR407899 doses versus placebo) and of the presence of angiographically successful PCI (YES/NO) as well as a continuous fixed covariate of baseline CFR. The corresponding interaction of order two will be also included in the model.
 
The final model will provide adjusted least-squares means (LS means)

	
estimates of the change from baseline to Week 4 in both treatment groups and their corresponding 95% confidence intervals. The difference of these estimates will be tested at the 5% 1-sided alpha level and the 95% confidence interval of the difference will be provided.
 
To evaluate the impact of missing values on treatment effect estimation, a multiple imputation method will be used.

	
Analysis of the key secondary endpoint:
 
The secondary analysis will use a similar model as primary analysis applied to the change from baseline to Week 4 in SAQ PL. The final model will provide adjusted least-squares means (LS means) estimates of the change from baseline to Week 4 in both treatment groups and their corresponding 95% confidence intervals. The difference of these estimates will be tested at the 10% 1-sided alpha level and the 95% confidence interval of the difference will be provided.
 
A safety review with a DMC meeting will start as soon as the first 19 patients will have been randomized and have finished the first week of treatment. Additional analyses for safety may be performed in this study.
 
Safety analysis:
 
Safety analyses will be descriptive, based on the safety population with a focus on BP, creatinine and cystatin C.
 
The safety analysis will focus on the TEAE period. This period is defined as the time from the first administration of the IMP to the last administration of the IMP +5 times the half-life. The half-life being from 20 to 31 hours depending on the age of the patients, a conservative estimate of 31 hours is used for all patients (thus 5 times the half-life corresponds to 5 times 31 hours ie, approximately 7 days).
 
Pharmacokinetic analysis:
 
Descriptive statistics will be provided by SAR407899 dose and time-point for observed concentrations.
 
Pharmacokinetic/pharmacodynamic analysis:
 
Scatter plots of concentrations versus primary/secondary endpoints will be provided. If relevant, some models will be provided to fit the relationship between concentrations and endpoint(s).

DURATION OF STUDY PERIOD (per patient)
	
 • Screening: up to 4 weeks before the first dosing (Day -28 to Day -1) and up to 6 weeks in patients diagnosed with MVA and stable angina without previous PCI who did not have a coronary artery angiography or CCTA in the previous 24 months but between 24 months and 5 years prior to screening and requiring CCTA in this screening period. • Titration phase: 3 weeks. • Maintenance phase: 1 week. • Total duration of treatment: 4 weeks (including titration). • Follow-up: 1 week. • Total study duration: 9 weeks (+/- 2 days) and up to 11 weeks (+/- 2 days) in patients requiring CCTA in screening period.

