8.3 METHOD OF ASSIGNING PATIENTS TO TREATMENT GROUP

At the screening visit, patients who will sign the informed consent form will be assigned an incremental subject number according to chronological order. The subject number remains unchanged during the study and allows the patient to be identified during the whole study. Stratification on the presence of angiographically successful PCI (YES/NO) will be performed.

The randomized treatment kit number list is generated centrally by Sanofi.

The IMPs are packaged in accordance with this list. The randomization and the treatment allocation (1:1) are performed centrally by an interactive voice/web response system (IVRS/IWRS). The IVRS/IWRS allocates treatment kits to the patient according to a prespecified randomization list, generated by the company in charge of the IVRS/IWRS.

A patient is considered as randomized as soon as the IVRS/IWRS has assigned a patient to active or placebo and indicated a treatment kit to be allocated to the patient, regardless whether the treatment kit was used or not (ie, patient registered by the IVRS/IWRS).

A patient cannot be randomized more than once in the study.

- All screening-failed patients will be entered in database with their subject number allocated at screening.

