11 STATISTICAL CONSIDERATIONS

11.1 DETERMINATION OF SAMPLE SIZE

The sample size calculations are based on the primary efficacy variable of uncorrected global CFR assessed by ¹³N-ammonia or ⁸²Rubidium PET scan change from baseline to Week 4.

Assumptions for sample size calculation:

- A large study of 2783 patients referred for rest/stress positron emission tomography suggested a SD 0.65 for CFR at baseline. With the hypothesis of correlation of 0.6 between baseline assessment and Week 4 assessment the SD for the change of baseline to week for could be estimated at 0.58
- A t-test at a 1-sided 5% significance level.

Based on the above assumptions, 35 evaluable patients per arm are needed for this study to detect a treatment effect of 0.35 with 80% of power. 10% more patients will be randomized in each group. Thus, approximately 78 patients will be randomized in this study, 39 per arm.

Calculations were made using East 6.3.

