11.4.2 Analyses of efficacy endpoints

11.4.2.1 Analysis of primary efficacy endpoint

Model assumptions for normality will be explored prior to the analysis testing.

Assuming that the change in CFR from baseline to Week 4 distribution is normal, an analysis of covariance (ANCOVA) model including the two following fixed categorical effect: treatment group (pooled SAR407899 doses versus placebo) and the presence of angiographically successful PCI (YES/NO) as well as a continuous fixed covariate of baseline CFR will be fitted. The interaction factors will be explored. The final model will provide adjusted least-squares means (LS means) estimates of the change from baseline to Week 4 in both treatment groups with their corresponding 95% confidence intervals (CIs). The difference of these estimates will be tested at the 1-sided 5% level using an appropriate contrast statement and the 95% confidence interval of the difference will be provided.

Let μ_0 and μ_1 be the population means of the change from baseline to Week 4 in CFR under placebo and SAR407899, respectively. The null hypothesis that will be tested is:

$H_0: \mu_0 = \mu_1$ versus $H_1: \mu_0 \neq \mu_1$.

Robustness of this statistical method will be assessed via sensitivity analyses detailed in the Statistical Analysis Plan (SAP), including different methodologies for missing data (multiple imputation and potentially pattern mixture modeling).

In this primary analysis, the mITT population is considered and the Week 4 assessments will be used regardless of whether the patient has previously discontinued the treatment.

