11.4.2.2 Analyses of secondary efficacy endpoints

The score of the SAQ-Physical Limitation scale will be derived according to the SAQ scoring instructions.

Assuming that the change from baseline to Week 4 in SAQ-Physical Limitation score distribution is normal, a similar model as primary analysis will be fitted. The interaction factors will be explored. The final model will provide adjusted least-squares means (LS means) estimates of the change from baseline to Week 4 in both treatment groups with their corresponding 95% confidence intervals (CIs). The difference of these estimates will be tested at the 1-sided 10% level using an appropriate contrast statement and the 95% confidence interval of the difference will be provided.

In this analysis, the mITT population is considered and the Week 4 assessments will be used regardless of whether the patient has previously discontinued the treatment.

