# **1 STATISTICAL AND ANALYTICAL PROCEDURES**

## **1.1 INTRODUCTION**

The purpose of this document is to provide additional technical details.

A comprehensive and detailed description of strategy and statistical technique used to perform the analysis of data was provided in Section 11 of the protocol (amended clinical trial protocol no 03 dated 18-Apr-2018).

Adverse events will be coded according to the Medical Dictionary for Regulatory Activities (MedDRA version 21.0).

Previous and concomitant medication records will be coded according to the World Health Organization Drug Dictionary (WHO-DD version 2018 MARCH 1).

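### Does the disagreement between synopsis and Section 11 over an interaction term leave the primary ANCOVA undefined?

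*Protocol*

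**What the plan says.** The synopsis (Clinical Trial Summary, statistical considerations) lists treatment group, PCI status and baseline CFR, and then states: "The corresponding interaction of order two will be also included in the model". The wording is singular, and the pair of terms is not named. The next sentence takes the LS means and the one-sided 5% test from a final model.

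Protocol Section 11.4.2.1 names the same three terms, "as well as a continuous fixed covariate of baseline CFR will be fitted. The interaction factors will be explored". It continues: "The final model will provide adjusted least-squares means (LS means) estimates of the change from baseline to Week 4 in both treatment groups". It gives no rule for keeping or dropping an explored interaction and no weights for the LS means if one is kept.

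For SAQ-PL the pattern repeats. The synopsis says "The secondary analysis will use a similar model as primary analysis applied to the change from baseline to Week 4 in SAQ PL", and Section 11.4.2.2 says "a similar model as primary analysis will be fitted. The interaction factors will be explored".

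Section 8.3 states that "Stratification on the presence of angiographically successful PCI (YES/NO) will be performed", with no expected share or quota. SAP Section 1.1 says of the protocol: "A comprehensive and detailed description of strategy and statistical technique used to perform the analysis of data was provided in Section 11". SAP Section 1.2 and Table 1 then replace both efficacy models with descriptive tables and listings after early termination.

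**The concern.** Including an interaction and exploring interactions are different instructions for the same hypothesis test. Three pairs are possible: treatment by PCI, treatment by baseline, and PCI by baseline. A statistician working from the synopsis and one working from Section 11 could test treatment in different models, and no sentence says which text prevails.

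Two things could be at stake. First, if a treatment-by-PCI term enters and the LS means weight the two strata equally, the treatment contrast becomes less precise when the strata are unequal, and power falls. Second, if the term is kept or dropped after looking at the data, the one-sided type I error can drift above 5%. The SAQ-PL analysis inherits the same question.

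**Working it through.** **Inputs from the documents** (synopsis and Section 11.1): baseline SD 0.65, correlation 0.6, SD of change 0.58, difference 0.35, one-sided 5%, 35 evaluable per arm, 10% inevaluable.

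**Assumptions, not in the documents:** the interaction is treatment by PCI; the strata are weighted equally; the PCI share is p; the true effect is the same in both strata.

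**1. The plan's own figure.** The SD of change is 0.65 × √(2 × (1 − 0.6)) = 0.581. A one-sided t-test with SD 0.58 has power 79.3% at 34 per arm and 80.4% at 35. Then 35 / 0.9 = 38.9, so 39 per arm and 78 in total. The stated "35 evaluable patients per arm are needed for this study to detect a treatment effect of 0.35 with 80% of power" reproduces. That calculation contains neither a PCI term nor an interaction.

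**2. Residual SD under ANCOVA.** Adjusting for baseline gives 0.65 × √(1 − 0.6²) = 0.52. With four model parameters, the additive model has power 87.3%. With SD 0.58 it has 80.3%.

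**3. Variance with a treatment-by-PCI term.** With n per arm, the treatment difference has variance 2σ²/(np) in one stratum and 2σ²/(n(1 − p)) in the other.

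- Equal weights: ¼ × [2σ²/(np) + 2σ²/(n(1 − p))] = (2σ²/n) × 1/(4p(1 − p)).
- Observed-share weights: p² × 2σ²/(np) + (1 − p)² × 2σ²/(n(1 − p)) = 2σ²/n, the same as in the additive model.

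So a loss arises only with equal weights and p away from one half.

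**4. Power with equal weights** (noncentral t, five parameters, 35 per arm):

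| PCI patients per arm | Variance factor | Power, SD 0.52 | Power, SD 0.58 |
|---|---|---|---|
| 17 | 1.00 | 87.3% | 80.3% |
| 12 | 1.11 | 84.1% | 76.6% |
| 10 | 1.23 | 80.9% | 73.0% |
| 7 | 1.56 | 72.0% | 63.8% |
| 4 | 2.47 | 55.1% | 47.8% |

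The result is symmetric in p and 1 − p. Simulation with 100,000 trials per share (SD 0.52, baseline CFR truncated at 2.0, assumed pre-truncation mean 1.75 and lower bound 0.5) gives 86.8%, 80.4%, 71.5% and 54.4% at 17, 10, 7 and 4 patients. With observed-share weights it gives 86.8 to 87.0%.

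**5. Type I error under an assumed selection rule.** The protocol states no rule. Suppose the term is kept when its p-value is below 0.10. With 400,000 null trials per share, the one-sided error with equal weights is 5.0%, 5.5%, 6.1% and 6.9% at 17, 10, 7 and 4 PCI patients per arm. With observed-share weights it is 5.0 to 5.1%. The additive model stays at 5.0%.

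**6. Which text governs.** The synopsis is a summary. SAP Section 1.1 points to Section 11 for the full method, and SAP Table 1 lists its changes against Sections 11.4.2.1 and 11.4.2.2, not against the synopsis. Section 11.4.2.1 specifies three terms and mentions exploration separately. Read alone, it gives an additive model, in which the stratum weights cancel from the treatment difference.

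**7. What is actually run.** SAP Section 1.2 reports 10 patients randomized and 8 with a post-baseline CFR. No model is fitted to CFR or SAQ-PL.

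**The case for a change.** The strongest case for a change is that the conflict sits in the test of the primary hypothesis, where the model should be fixed before unblinding. No sentence gives Section 11 precedence. Calling it comprehensive does not withdraw the synopsis, and Section 11 refers to a final model straight after promising exploration. The SAP removes the model without settling its form. The repair would be a few words and would cost no patients, data or exploratory work.

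Much of this stands. The two texts do differ, Section 11 does leave its final model undefined, and one additive model stated in both places would be cleaner.

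Two points do not stand in full. The synopsis, read plainly, does put an interaction in its model; what it lacks is the name of the term. The silence on whether an interaction may enter therefore belongs to Section 11 alone. Nor is there a fixed stratum size below which power drops under 80%. With residual SD 0.52, equal-weight power is still 80.9% at 10 PCI patients per arm; with SD 0.58 it is already 76.6% at 12. The harm needs several conditions together, none of them stated in the documents.

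**Conclusion.** This is a minor inconsistency in the protocol text, and no change to the plan follows. The SAP's descriptive analysis replaces both models, so aligning the wording would alter no estimate, test or conclusion. Had the trial run to 78 patients, an analyst following Section 11 would most naturally have fitted treatment, PCI stratum and baseline value, with power of 80 to 87% at 35 evaluable per arm and the nominal 5% error.

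The worst cases computed, power of about 48 to 55% and type I error of 6.9% at 4 PCI patients per arm, depend on assumptions: a treatment-by-PCI term, equal stratum weights, a PCI share of about 11% and, for the type I error, a p<0.10 retention rule. With balanced strata or observed-share weights neither problem appears. The power figures also assume no true interaction and the protocol's SD and correlation.
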